7.2.1.2 Symptomatology

At each study visit, Subjects will be asked about their symptoms as reported during the Screening period and Visit 1. Changes in symptoms severity will be recorded in the source documentation.

7.2.1.3 Other

At each visit subjects will be asked to complete a Functional status – New York Heart Association Class questionnaire. This questionnaire will be used to assess changes in their quality of life.

7.2.1.4 Electrocardiogram (ECG)

An ECG will be performed for safety at Visit 1 and Visit 3.

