The experience with long term use of a combination of three antibiotics in *Mycobacterium avium paratuberculosis* and Crohn's disease has been largely in younger subjects who did not receive anti-platelet agents as concomitant therapies, and thus, macrolide anti-platelet agent interactions have not been observed. In the proposed group of subjects with CHD disease, clarithromycin has a known interaction with anti-platelet agents and therefore in this group, clarithromycin will be substituted by azithromycin, a similar macrolide that demonstrates the same intracellular activity against *C.*

pneumoniae but does not exhibit such interaction with anti-platelet agents. The azithromycin dose will be reduced due to its longer half-life, resulting in longer bioavailability duration in the body. Due to reported occasional QT-prolongation at high doses of azithromycin, ECG monitoring of the QT-interval will be carried out.

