5. STUDY PRODUCT

5.1 Dosage Schedule

The treatment will be administered as 50mg capsules of doxycycline, 250mg capsules of azithromycin and 150mg of rifabutin twice daily (morning and evening). The total number of capsules taken is 3 capsules a day in the first week then 6 capsules a day to be taken after food, with plenty of fluids, until the end of dosing period.

The treatment is to be on a dose escalation schedule, taken as per the following schedule:

Week 1 (Day 1 to Day 7)

Time	Doxycycline	Azithromycin	Rifabutin
Breakfast	50mg	250mg	150mg
Dinner			

Week 2 until EOT (Day 8 to Day 90)

Time	Doxycycline	Azithromycin	Rifabutin
Breakfast	50mg	250mg	150mg
Dinner	50mg	250mg	150mg

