7.1.2 Visit 2 (Day 30 ± 7)

At this visit the subject will be asked to report on current symptoms, changes to concomitant medications, and adverse events. A blood sample will be collected for laboratory tests. Subject will undergo a complete physical examination. The following assessments will also be performed:

- FBC, ESR and EUC
- LFT and Lipid Studies
- CK-MB, high sensitivity Troponin T
- High sensitivity CRP
- ECG
- Physical examination
- Vital Signs
- Symptomatology record
- Functional status – New York Heart Association Class

Subjects will be required to bring their medication with them for assessment of compliance.

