7.1.3 Visit 3 – End of Treatment (Day 90 ± 21)

At this visit the Subject will be asked to report on current symptoms, changes to concomitant medications, and adverse events. A blood sample will be collected for laboratory tests. Subject will undergo a physical examination. The following assessments will also be performed:

- FBC, ESR and EUC
- LFT and Lipid Studies
- CK-MB, high sensitivity Troponin T
- High sensitivity CRP
- *Chlamydophila pneumoniae* macrophage cultures
- *C. pneumoniae* titer measurement
- *C. pneumoniae* DNA detection using LAMP
- Symptomatology record
- Physical examination
- Vital Signs
- ECG
- Angiogram
- Fractional Flow Reserve Study and pressure/flow measurements
- IVUS and OCT of culprit and non-culprit arteries (sub-study)
- Functional status – New York Heart Association Class

The Subject will be required to return all unused medication, and all used empty packaging for assessment of compliance. Subjects will also be required to return diaries for review and collection.

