7.2.2 Safety data

7.2.2.1 Laboratory Studies

A blood sample will be collected at each visit. The following blood tests will be performed: Full blood count, Full biochemistry as per detailed in 7.2.1.1. Additional tests may also be requested by the physician, but will not be part of the study unless related to adverse events.

The reference ranges for normal laboratory values and current certificate of NATA accreditation will be obtained from the relevant laboratories before the study commences.

Values outside the normal range will be noted in the CRF and those considered to be of clinical significance, particularly those related to the study medication, will be recorded as adverse events. Values outside the normal range will be monitored until they have been stabilised.

Comparison of pre and post treatment C. pneumoniae parameters will be assessed to show efficacy of the ACAC combination.

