9. WITHDRAWALS AND DEFAULTERS

Subjects may be withdrawn from study medication for the following reasons:

- Determined to be necessary as per investigator, including:
 - Due to AE or SAE
 - Development of any exclusion criteria may be cause for discontinuation
 - Treatment with prohibited medications
 - Female participants fall pregnant or female partners of male participants fall pregnant
 - Subject lost to follow up (does not complete all Study visits and Study staff have failed to make contact with the subject nor arrange a successful visit for a period of 1 month past a scheduled Study visit).
 - If, in the investigators opinion continuation in the study would be detrimental to the subjects well-being

- Subjects are free to withdraw consent at any time.

In all cases the reason for withdrawal, if given, must be recorded in the Case Report Form and in the subject's medical records. The subject must be followed up to establish whether the reason was an adverse event, and if so, this must be reported in accordance with the procedures in section 8 Adverse Events.

Every effort will be made to follow up subjects who withdraw or are withdrawn from the study. All subjects withdrawn or who choose to withdraw consent will be asked to return to the study site to undergo final EOT study procedures, or as far as possible, all safety examinations scheduled for the final EOT visit for all subjects who taken at least one dose of the study drug/s. This is especially important for those subjects who withdraw due to AEs or SAEs, in order to allow for collection of detailed safety data in accordance with the procedures in section 8 Adverse Events. These subjects should be given appropriate care under medical supervision until the symptoms of any AE resolve, or the subject's condition becomes stable. Subjects may then be contacted at the end of the study for final safety monitoring procedures.

While primary analysis will be of all consenting subjects, a secondary 'on-treatment' analysis will be performed on subjects who remain compliant at the end of the 90-day endpoint.

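### The protocol disagrees with itself on the Visit 2 ECG; under the schedule table and 7.2.1.4, the first planned post-baseline ECG comes at End of Treatment, too late to inform dosing

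*Combined protocol and SAP*

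**What the plan says.** Four places in the protocol bear on this.

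- Section 1.2 gives the purpose: "Due to reported occasional QT-prolongation at high doses of azithromycin, ECG monitoring of the QT-interval will be carried out". It also says that the azithromycin dose is reduced in this trial.
- Section 7.1.2 includes the ECG among the assessments to be done at Visit 2. The consecutive items in its list read "High sensitivity CRP - ECG - Physical examination".
- The ECG row of the study schedule table is marked under V1 and V3, with the V2 cell blank.
- Section 7.2.1.4, the section devoted to the ECG, says: "An ECG will be performed for safety at Visit 1 and Visit 3".

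On treatment status, section 7.1.2 says of Visit 2 that "Subjects will be required to bring their medication with them for assessment of compliance", so the subject is still on drug. Section 7.1.3 describes Visit 3 as End of Treatment and says: "The Subject will be required to return all unused medication, and all used empty packaging for assessment of compliance".

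**The concern.** A site cannot follow all three scheduling instructions, and the protocol does not say which prevails. Two sites could each point to protocol text and still differ on whether a subject has any planned QT reading during treatment.

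This matters because the ECG is the safeguard the protocol itself names for a known azithromycin risk. Visit 2 is the only clinic visit between baseline and End of Treatment. Without an ECG there, the Visit 3 ECG can describe a QT effect after the fact, but no planned ECG after baseline can support a decision to stop the drug.

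**Working it through.** The protocol states no figure to reproduce. The check compares the sections and then counts days.

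**Is the blank V2 cell real?** The neighbouring table rows (physical examination, vital signs, NYHA class) keep their V2 marks, and 7.2.1.4 repeats the V1 and V3 pattern in words. The blank is not a text-extraction fault.

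**Inputs**
- Full dose: Day 8 to Day 90, after one week at half dose (section 5.1).
- Visit 2: Day 30 ± 7 (7.1.2), or Day 30 with +7 only (table).
- Visit 3: Day 90 ± 21 (7.1.3), or Day 90 with +21 only (table).
- Day 60: phone call (table).

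**Counting rule (an assumption).** Dosing ends at Day 90 or at the Visit 3 drug return, whichever comes first. Full-dose days up to and including day d are d − 8 + 1. Scheduled days left are 90 − d.

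**Visit windows**
- Visit 2: 30 − 7 = Day 23 to 30 + 7 = Day 37 by 7.1.2; Day 30 to 37 by the table.
- Visit 3: 90 − 21 = Day 69 to 90 + 21 = Day 111 by 7.1.3; Day 90 to 111 by the table.

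**With a Visit 2 ECG**

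| ECG day | Full-dose days so far | Days left to Day 90 |
|---|---|---|
| 23 | 23 − 8 + 1 = 16 | 90 − 23 = 67 |
| 30 | 30 − 8 + 1 = 23 | 90 − 30 = 60 |
| 37 | 37 − 8 + 1 = 30 | 90 − 37 = 53 |

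If Visit 3 and the drug return fall on Day 69, the earliest 7.1.3 allows, the days left after Visit 2 are 69 − 37 = 32 to 69 − 23 = 46.

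**Without a Visit 2 ECG.** The first planned post-baseline ECG is at Visit 3. Full-dose days by then are 69 − 8 + 1 = 62 for a Day 69 visit and 90 − 8 + 1 = 83 for a visit at Day 90 or later. Days left are 0 in every case, because the visit itself ends treatment.

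**The case against.** The strongest reply is that the Visit 2 ECG is already in the protocol. A site working from the visit-by-visit instructions will do it, so what remains is a missing table mark and a missing word, and nothing shows that either site follows the other version. That is fair, and it limits the point to an inconsistency. It does not remove it, because the table and the section devoted to the ECG both say otherwise.

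Other objections:

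- **Deleting the ECG from 7.1.2 would also restore consistency.** It would, and section 1.2 gives no timing and ties QT prolongation to high doses. But deletion would leave the promised monitoring with no planned reading while the drug can still be stopped. The purpose in 1.2 and the existing entry in 7.1.2 favour adding Visit 2.
- **Dosing might run past Day 90.** Section 5.1 refers to EOT as well as Day 90, and 5.2 supplies extra drug for the visit window. If dosing ran to a Day 111 Visit 3, full-dose days would reach 111 − 8 + 1 = 104, and the days left after a Day 23 ECG would be 111 − 23 = 88. The upper bounds above therefore depend on the counting rule. The zero after Visit 3 does not.
- **Physicians can order tests anyway.** Section 7.2.2.1 says: "Additional tests may also be requested by the physician, but will not be part of the study unless related to adverse events". That sentence sits under laboratory studies and is discretionary, so it is not scheduled QT monitoring.
- **A Visit 2 ECG brings no QTc threshold or action rule.** This stands. The correction makes a reading available in time but does not say what to do with it.

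**Conclusion.** The concern holds. Section 7.1.2 conflicts with the schedule table and 7.2.1.4 in the current text. At nominal days the difference is a first planned post-baseline ECG at Day 30 with 60 scheduled dosing days left, against Day 90 with none. Across the 7.1.2 window, 53 to 67 days are left (32 to 46 if Visit 3 falls on Day 69). These counts assume that dosing ends at Day 90 or at the Visit 3 drug return, whichever comes first. The conclusion that nothing is left after Visit 3 needs only that Visit 3 ends treatment.

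This is a limited safety correction that should be made. It changes no estimate, test or analysis population, and it is not evidence that QT harm would go undetected.

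**What to change.** 1. Mark the ECG under V2 in the study schedule table.
2. Change 7.2.1.4 to name Visit 1, Visit 2 and Visit 3, so that it matches 7.1.2.
3. Add a line to 7.1.2 that the investigator reviews the Visit 2 ECG for QT while the subject is still on drug.

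Any action then uses the discretion that section 9 already gives: "Subjects may be withdrawn from study medication for the following reasons", with investigator judgement and adverse events among the grounds listed. Naming the ECG in the synopsis safety data and in 7.2.2 would help clarity but is optional.

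The cost is wording, plus at most one extra ECG and its reading per subject, and only where a site now follows the table. That is at most 60 ECGs among the 60 completers, plus one for each subject who attends Visit 2 but does not complete. No new visit or type of procedure is needed.

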7.2.1.5 Fractional Flow Reserve (FFR) Study

The results will assess the physiological effect of arterial stenosis.

Fractional Flow Reserve study is a guide wire based procedure to measure changes in blood pressure and flow across non-critical lesions in the coronary arteries performed at the time of a diagnostic or interventional coronary procedures. The results will assess the degree of arterial stenosis. This is a common clinically indicated procedure, which will be performed at

baseline and at Visit 3. Additional measurements of coronary flow as measured with the FFR pressure/flow guidewire will be recorded in the culprit and non-culprit artery at the time of FFR measurement.

7.2.1.6 Intra-coronary Imaging (IVUS and OCT) Sub-study

The results will assess the anatomic extent and morphology of atherosclerosis and response to treatment.

Intra-coronary imaging (IVUS and OCT) are catheter based imaging techniques allowing direct visualisation and characterisation of coronary plaque in vivo in addition to assessment of coronary arteries and stent expansion pre and post stent implantation. Indications for use are to determine lesion characteristics and to guide stent implantation. The results will be used to assess plaque volume and morphology and response to therapy.

7.2.2 Safety data

7.2.2.1 Laboratory Studies

A blood sample will be collected at each visit. The following blood tests will be performed: Full blood count, Full biochemistry as per detailed in 7.2.1.1. Additional tests may also be requested by the physician, but will not be part of the study unless related to adverse events.

The reference ranges for normal laboratory values and current certificate of NATA accreditation will be obtained from the relevant laboratories before the study commences.

Values outside the normal range will be noted in the CRF and those considered to be of clinical significance, particularly those related to the study medication, will be recorded as adverse events. Values outside the normal range will be monitored until they have been stabilised.

Comparison of pre and post treatment C. pneumoniae parameters will be assessed to show efficacy of the ACAC combination.

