The presence of *C. pneumoniae* in atheromatous plaque specimens and in vitro animal models have implicated *C. pneumoniae* as a potential infectious agent in the pathogenesis and progression of CAD particularly as there is no commensal form of *C.pneumoniae*. *C. pneumoniae* is a common cause of pneumonia and respiratory infection worldwide and has been shown to infect and propagate in human

smooth muscle and endothelial cells of coronary arteries which can be cultured from circulating macrophages. Antibodies to *C. pneumoniae* have been detected in elevated levels in subjects with atherosclerosis though this is non-specific. Some suggest that coronary arterial infection stems from the migration and proliferation of infected macrophages into the intimal layer of the arterial wall after an initial functional alteration or injury to the endothelium⁹.

While numerous studies have demonstrated the presence of *C. pneumoniae* in atherosclerotic arteries and endarterectomy specimens, a lack of standardisation of current diagnostic methods may be responsible for inconsistent detection of *C. pneumoniae*. Indeed detection methods have been largely concentrated on serological studies due to the complexity and difficulty in obtaining tissue cultures. However, accumulating evidence indicates that detection through serological investigations has not been as specific as previously assumed¹⁰. Although cell culture studies remain the gold standard in *C. pneumoniae* detection, isolation and proliferation of *C. pneumoniae* in tissue samples remain a difficult problem resulting in inconsistent results¹¹.

Current Treatment

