4. SELECTION OF STUDY POPULATION

4.1 Inclusion Criteria

The subject must meet all of the following criteria to be eligible for inclusion in the study:

1. Males and females (without childbearing potential as evidenced by hysterectomy, tubal ligation or at least one year post-menopause) aged 18 to 80 years, inclusive.
2. Ability to provide written informed consent to participate in the study.
3. Subjects with documented recent acute coronary syndrome (ACS) or evidence of myocardial ischemia.
4. Subjects who have a culprit lesion suitable for PCI, and a non-critical lesion in another vessel suitable for staged PCI with an FFR of ≤ 0.80 , for subjects undergoing diagnostic angiography and FFR without ad hoc PCI. Or subjects who have a single non-critical culprit lesion of intermediate severity with a clinically indicated FFR ≤ 0.80 which is suitable for staged PCI.
5. No serious co-morbidities, which might interfere with the subject's ability to enter the study.
6. Able to communicate effectively with the study team and to comply with the protocol.

4.2 **Exclusion Criteria**

The subject must be excluded for any of the following reasons:

1. Females that are of child bearing potential
2. Subjects without a non-culprit lesion considered appropriate to plan a staged PCI.
3. Clinically significant haematologic, hepatic, metabolic, renal, rheumatologic, anaphylactic reactions, neurological or psychiatric disease
4. Clinical evidence of any other disease, which might interfere with the subject's ability to enter the trial.
5. Concomitant administration of medications that may interfere with treatment as assessed by the Investigator, including allergy to any component of the therapy.
6. Concomitant administration of any medication prohibited for use during this study (e.g. colchicine)
7. Male subjects consuming greater than 60g alcohol per day, or female subjects consuming greater than 40g alcohol per day.
8. Evidence of any recent history of, or current recreational drug abuse
9. Serious adverse reaction or hypersensitivity to therapeutic drugs.
10. Unable and to comply with the study requirements.
11. Subjects who have been involved in an experimental drug protocol within the past four weeks.

A list of subjects screened but deemed ineligible will be maintained indicating reason(s) for exclusion.

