7.2.1.1 Laboratory Studies

Efficacy of combination therapy will be assessed using blood samples collected at each visit. The following tests will be performed: FBC, ESR, lipid studies, liver function. In addition the following will be performed:

High Sensitivity C-Reactive protein (Hs-CRP) is a protein in the blood that increases in the presence of inflammation. Hs-CRP will measure the small amounts of CRP produced by the long-term inflammation from atherosclerosis.

- 4ml of blood will be collected in an EDTA tube. This sample will then be transferred to the laboratory for a full blood count
- 4ml of blood will be collected in an SST/Gel tube and transferred to the laboratory for liver function tests, Cholesterol, triglyceride studies and hs-CRP.
- 4ml of blood will be collected in a lithium heparin tube. Sample will then be transferred to the laboratory for CK-MB, Troponin T tests and UEC testing.
- 5ml of blood will be collected in a special ESR collection tube. This will then be sent to the laboratory to test the ESR
- 2 x 4ml of blood will be collected in citrated tubes. This sample will be transferred to the laboratory for *C. pneumoniae* detection by macrophage culture and *C. pneumoniae* titer determination (Visit 1 and 3 only).
- 3 x 4ml (i.e. 12 ml) of blood will be collected in an EDTA tube. This sample will be transferred to the laboratory for *C. pneumoniae* DNA detection by LAMP (Visit 1 and 3 only).

The total blood drawn on at Visit 1 and Visit 3 will be approximately 40mls. The total blood drawn at Visit 2 will be approximately 20 ml.

Blood samples will be tested by an experienced pathologist at Lavery Pathology for all tests excluding *C. pneumoniae* DNA detection by LAMP (exploratory research) and *C.pneumoniae macrophage cultures*.

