11. STATISTICAL PROCEDURES

11.1 *Analysis Variables*

Analysis of efficacy will be performed according to intention-to-treat method and include all subjects who received the combination antibiotic therapy. However as the primary efficacy analysis is of subjects with paired FFR assessments, only such subjects will be included in the primary analysis. All other subjects will be included in secondary analyses. Numerical data will be presented as mean \pm SD for normally distributed variables and as median with interquartile range for non-normally distributed data. Non-normally distributed data will be log-transformed (e.g. CRP levels) before being used for comparisons. Significant changes in subjects' arterial flow, clinical symptoms and biochemical variables over time compared with that baseline will be assessed using an analysis of covariance. Differences between treatment and control groups in the occurrence of FFR \geq 80 will be assessed using Fisher's exact test. All tests will be 2-tailed with a 5% significance level.

11.2 *Interim Analysis*

A DSMB directed interim analysis is planned when 60 paired FFR data are available. At this time point, the trial would declare the combination therapy as effective if the p value is less than 0.05. However, the trial might still continue to collect extra data to accurately characterise side effects as advised by the DSMB.

11.3 *Sample Size Justification*

This is a feasibility study designed to provide preliminary observations and generate hypothesis for future studies. The sample size of 60 subjects with paired FFR was not defined on the basis of a clinical endpoint hypothesis but rather to provide information about antibiotic combination therapy efficacy and safety. The sample size required is established by assessment of the minimum number of subjects needed to provide reliable and non-trivial results. The sample size is in the range of the intervention group in the azithromycin clinical trial of subjects with CAD (n=60).

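### The C. pneumoniae pre/post change is said to show efficacy, but it is not a randomised comparison and it includes subjects with nothing detectable to clear

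*Combined protocol and SAP*

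**What the plan says.** Section 7.2.2.1, which sits under the safety data, states: "Comparison of pre and post treatment C. pneumoniae parameters will be assessed to show efficacy of the ACAC combination". The synopsis also lists titer, macrophage culture and DNA detection under efficacy data. Section 7.2.1.1 limits all three assays to Visits 1 and 3.

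None of the six inclusion criteria in Section 4.1 or the eleven exclusion criteria in Section 4.2 mentions C. pneumoniae. The disease criterion is "Subjects with documented recent acute coronary syndrome (ACS) or evidence of myocardial ischemia", together with lesion and FFR requirements. Randomisation takes place at the screening visit (Section 4.5), where the first sample is drawn (Section 7.1.1), and does not depend on the result.

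Section 11.1 sets the efficacy population: "Analysis of efficacy will be performed according to intention-to-treat method and include all subjects who received the combination antibiotic therapy". Its nearest method is for "biochemical variables over time compared with that baseline will be assessed using an analysis of covariance", while the synopsis names repeated-measures ANOVA. Section 11.1 assigns Fisher's exact test to FFR. No test is named for the C. pneumoniae results. Positivity and clearance are not defined, and there is no rule for subjects negative at baseline.

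Section 1.1 says that "a lack of standardisation of current diagnostic methods may be responsible for inconsistent detection of" the organism. It also describes culture from tissue as difficult and inconsistent, and raised antibody levels as non-specific.

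**The concern.** There are two gaps.

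First, a change from before to after treatment has no control. Subjects can turn from positive to negative without the drug, for example through natural course or an inconsistent assay. The trial has a randomised placebo arm, but Section 7.2.2.1 does not use it.

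Second, negative subjects can be enrolled, and the protocol's own account of detection makes them likely. A subject negative at Visit 1 cannot show clearance. If results are summarised as a clearance rate or mean change over all subjects, the effect shrinks by the baseline-positive share. A null result could then not be told apart from few subjects having had detectable organism.

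The regimen is named and justified as anti-Chlamydophila, and these assays are the only direct readout of whether it acts on the organism. An unsound comparison could mislead in either direction about mechanism.

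**Working it through.** **Inputs from the protocol.** 60 subjects with paired FFR, 1:1 allocation (Section 3), two-sided 5% level (Section 11.1). The protocol states no figure for the C. pneumoniae comparison. Its own size figures reproduce: 60/(1 − 0.25) = 80 approached, and 20% of 30 per arm = 6. I use 30 per arm.

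**Assumptions not in the protocol.** Baseline-positive share π, varied. Among positives, 20% turn negative on placebo and, where an ACAC rate is needed, 70% on ACAC. No new positives and a perfect assay.

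**Step 1: pre/post change in the placebo arm alone.** With every discordant pair running from positive to negative, the exact two-sided McNemar p-value is 2 × 0.5^d for d such pairs. At d = 5, p = 0.0625; at d = 6, p = 0.031. The test therefore rejects at d ≥ 6. With d ~ Binomial(30, 0.20 × π):

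| π | 0.20 × π | P(p < 0.05), placebo arm |
|---|---|---|
| 0.25 | 0.05 | 0.3% |
| 0.50 | 0.10 | 7% |
| 0.75 | 0.15 | 29% |
| 1.00 | 0.20 | 57% |

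Only the product of the two assumed rates matters, so the table also covers other pairs with the same product. An ACAC arm in which the drug did nothing would reject equally often. New positives would lower these figures.

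**Step 2: shrinkage of an all-subject effect.** If negatives stay negative, all-subject difference = π × (difference among positives). With 70% − 20% = 50 points among positives:

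- π = 0.25: 0.25 × 50 = 12.5 points
- π = 0.50: 25 points
- π = 0.75: 37.5 points
- π = 1.00: 50 points, no shrinkage

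This applies to a rate or a mean change. It does not apply to the McNemar p-value: with discordant pairs 8 v 1, p = 0.039 whether 0, 10 or 20 negative-to-negative subjects are added.

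**Step 3: does restricting to baseline-positives gain power?** Power for ACAC v placebo under the same assumptions. Fisher figures are by exact enumeration; the baseline-adjusted figures are simulated.

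| π | Fisher, Visit 3 status, all subjects | Fisher, baseline-positives only (30 × π per arm) | Baseline-adjusted ANCOVA, all subjects |
|---|---|---|---|
| 0.20 | 9% | 16% | about 38% |
| 0.40 | 35% | 61% | about 71% |
| 0.60 | 61% | 83% | about 88% |
| 0.80 | 84% | 93% | about 95% |

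If the number of positives varies binomially in each arm, as it does in the ANCOVA simulation, the positives-only column becomes 26%, 62%, 83% and 94%. Simulated type I error for the ANCOVA was 3–5%. The loss in the first column comes from ignoring the Visit 1 result, not from including negatives.

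**The case against.** The strongest reply is that Section 7.2.2.1 says only that the parameters will be assessed. No test, population or pooling is written, so shrinkage is a risk of one way of filling the gap, not an error on the page. That stands, and so the size of the shrinkage is given only as a function of an unknown share.

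The nearest method in Section 11.1, analysis of covariance, uses baseline. Applied between arms in all subjects, it would have similar or higher power than a positives-only test (step 3). That also stands. A reader might infer that restricting to positives necessarily gains power; it does not.

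A reader might also infer that baseline-negatives cannot be scored. They can: both samples are taken, and each subject is negative-to-negative or newly positive. They are uninformative about clearance only. A quantitative titer can move in either direction in anyone.

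Nor is the missing infection criterion a design fault in itself. The primary endpoint is FFR, and the rationale does not need a positive test at entry.

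Finally, Section 11.1 could be read as confining efficacy to subjects who took the antibiotics. The same section compares treatment with control for FFR, so the documents do not establish that a single-arm efficacy analysis is intended.

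On weight, no primary or secondary objective concerns eradication, the only C. pneumoniae objective is exploratory and concerns LAMP as a detection method, and Section 11.3 calls this a feasibility study. That limits the point but does not remove it: the text still claims that the comparison will show efficacy.

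**Conclusion.** The point holds in a limited form. A pre/post change cannot show efficacy of ACAC, because it is not a randomised comparison. Under the illustrative assumptions, the placebo arm alone would give p < 0.05 in about 7% of trials at 50% baseline-positive, little above the nominal 5%, and in about 57% at 100%. Separately, baseline-negatives by culture or LAMP shrink any all-subject clearance rate or mean change by the baseline-positive share, which the documents do not give. Both sizes rest on assumed conversion rates, a perfect assay and no new positives. The importance is minor to moderate: the primary FFR analysis is not affected, but the stated method should be replaced, not merely described in more detail.

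**What to change.** Reword Sections 7.2.2.1 and 11.1 before unblinding:

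- Label the C. pneumoniae analysis exploratory and define a positive result for each assay.
- For culture and LAMP, compare ACAC with placebo on the proportion negative at Visit 3 among subjects positive at Visit 1 by that assay, with a confidence interval. Visit 1 status is a pre-treatment variable if the sample precedes the first dose, so conditioning on it keeps the randomised comparison.
- Tabulate baseline-negatives by arm as negative-to-negative or new positive, and report the baseline-positive share by arm.
- For titer, compare Visit 3 log titer between arms, adjusted for baseline log titer, in all subjects.
- As a sensitivity analysis for culture and LAMP, report a baseline-adjusted between-arm comparison in all subjects.

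The cost is wording only, with no new samples or visits. There are two downsides. The denominator for clearance is smaller: at 25% positive, about 8 per arm (30 × 0.25 = 7.5). False-negative Visit 1 tests, which Section 1.1 makes plausible, will leave some infected subjects out of the main clearance comparison; the sensitivity analysis is there for that reason.
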